**Table 1. Hepatic Function Categories Based on Child-Pugh Score**

Cohort	Description	Child-Pugh Score	Number of Participants
1	Without hepatic impairment	Not Applicable	6 a
2	Mild hepatic impairment	Class A (5 to 6 points)	6
3	Moderate hepatic impairment	Class B (7 to 9 points)	6
4	Severe hepatic impairment	Class C (10 to 15 points)	6 b

- Additional participants may be dosed to a maximum of 8 participants to ensure mean age  $\pm 5$  years and mean body weight  $\pm 10$  kg of this cohort is aligned with the pooled average assessed when  $\geq 75\%$  of participants are dosed across the other 3 cohorts.
- If recruitment across the sites selected proves to be prohibitive, study will dose only 4 participants in this cohort.

Categorization of participants into Cohort 2-4, inclusive, will be done based on Child-Pugh scores determined, as described in [Appendix 8](#) at the screening visit. Participants will be dosed in a staged manner such that those with moderate and severe hepatic impairment (Cohorts 3 and 4) will be evaluated first. Recruitment for participants with mild hepatic impairment (Cohort 2) will initiate when approximately 50% of the total participants in Cohorts 3 and 4 have been dosed. Participants without hepatic impairment (Cohort 1) will be recruited near the end of the study to match the average demographics (at a minimum, age and weight; and gender as much as practically possible) across the pooled Cohorts 2 through 4.

***Approval from the Sponsor must be obtained before proceeding with recruitment for participants in Cohort 1 and Cohort 2.***

Participants who prematurely discontinue before completing all assessments may be replaced, at the discretion of the principal investigator (PI) and sponsor study team.

The overall study design is summarized in [Section 1.2](#). For individual participants, the total duration of participation from the screening visit to the follow-up visit will range from approximately 5 weeks (minimum) to approximately 9 weeks (maximum).

#### **4.2. Scientific Rationale for Study Design**

This study involves participants with varying degrees of hepatic impairment and participants without hepatic impairment, matched for age as well as body weight (and gender as much as practically possible). A single dose of PF-06882961 is proposed, as single dose plasma PK of PF-06882961 is generally predictive of exposure upon repeated dosing and limited accumulation has been observed given the relatively short half-life of the compound.

Following administration of single doses of PF-06882961, the arithmetic mean terminal  $t_{1/2}$  of PF-06882961 ranged from 5-7 hours. Even with a possible modest increase in half-life, serial PK samples will be collected over 48 hours post-dose is expected to adequately characterize the elimination phase of the plasma concentration-time profile in the cohorts with varying degrees of hepatic function.

Based on a review of the effect of hepatic impairment on human pharmacokinetics for compounds cleared in a similar manner to PF-06882961 [CCI](#) mild hepatic impairment generally results in less than 2-fold increases in plasma exposure. In the same group of compounds, moderate hepatic impairment results in less than 3-fold increases in plasma exposure; however, overall, very limited clinical data are available regarding the effect of severe hepatic impairment [CCI](#) [15-17](#).

In this study, a single dose of PF-06882961 will be administered with a standard breakfast to reflect the conditions for anticipated use of PF-06882961 in the target T2DM population. Additionally, in study C3421001, variability based on geometric %CV for  $C_{max}$  was lower following administration with a high-fat meal (23% in the fed state, compared to 91% in the

fasted state). The adjusted geometric mean  $C_{max}$  was 57% lower (90% CI: 28%, 74%) in the fed state compared to the fasted state, while mean  $AUC_{inf}$  values were similar (approximately 12% lower in the fed state [90% CI: -5%, 26%]).

In general, participants with normal hepatic function (Cohort 1) will abstain from concomitant treatments, except for the treatment of adverse events. However use of selected limited prescription and non-prescription medications is permitted (refer to [Section 6.5](#) for details). COVID-19 specific assessments have been incorporated to minimize the risks of COVID-19 related complications to participants and the study site personnel.

Participants with impaired hepatic function (Cohorts 2, 3, and 4) are permitted to be on stable doses of background medications for the management of their concomitant medical condition(s) with some exclusions ([Appendix 9](#)).

The Child-Pugh classification (CPC; refer to [Appendix 8](#)) will be used to define the 3 cohorts of participants with varying degrees of hepatic impairment. This study will include participants with mild (Child-Pugh Class A, Cohort 2), moderate (Child-Pugh Class B, Cohort 3), and severe (Child-Pugh Class C, Cohort 4) hepatic impairment as well as demographic-matched control participants without hepatic impairment (Cohort 1). All 3 categories of hepatic impairment will be assessed. All participants will be required to provide their own consent to participate in this study, hence participants with clinically-active Grade 3 or Grade 4 encephalopathy will be excluded. However, participants who have a previous history of Grade 3 or 4 encephalopathy but are currently receiving an intervention [for example: lactulose or lactitol, alone or in combination with rifaximin, and/or neomycin] to manage their encephalopathy-related signs and symptoms are eligible provided the on-treatment encephalopathy grading at the screening visit is Grade 2 or lower thereby permitting them to provide their own informed consent. Acknowledging the medical state of the population enrolled, certain eligibility criteria for participants with hepatic impairment are distinctly different, with no specific exclusion of participants with Hepatitis B and Hepatitis C in Cohorts 2, 3, or 4.

As stated in [Section 2.2.2.2](#), there appears to be no clear effect of mild renal impairment on PF-06882961 pharmacokinetics. However, to enable a clearer assessment of the effect of hepatic impairment on PF-06882961 disposition, participants will be excluded if there is concomitant clinical evidence of renal impairment, defined as estimated glomerular filtration rate (eGFR) <60 mL/min.

Both women of childbearing potential, as well as those who are of non-childbearing potential, will be enrolled given the availability of embryo fetal developmental (EFD) toxicity studies with PF-06882961. However, as marketed GLP-1R agonists are listed as contraindicated in pregnancy, measures will be taken to limit the risk of pregnancy in the female population enrolled (see [SoA](#) and [Section 10.4](#)).

The potential risk of exposure to PF-06882961 in a sexual partner of a male participant in this study via ejaculate is low, and therefore no contraception (condom) use in male participants is warranted. The calculated safety margin is  $\geq$ 100-fold between the estimated partner exposure due to seminal transfer and the NOAEL for serious manifestations of developmental toxicity in nonclinical studies. The safety margin of 100-fold is based on applying a 10-fold safety factor for interspecies extrapolation and a 10-fold safety factor for susceptible populations.

Banked Biospecimens will be collected and stored for further analyses which may, for example, provide greater understanding of the study intervention.

#### **4.3. Justification for Dose**

Based on data available from the completed C3421001 study, a single dose of PF-06882961 20 mg is expected to be safe and well tolerated and will provide data to meet the objectives of this study. This dose selection also takes into account safety considerations for patients with varying degrees of hepatic impairment in whom an increase in plasma concentration of PF-06882961 may be observed in this study. Based on current Phase 1 data, a 20 mg dose is anticipated to be well tolerated. Since the exposure of PF-06882961 is approximately dose-proportional over the range of clinical doses (up to single dose of 300 mg and up to 120 mg BID), the results of this study can be extrapolated to understand the effect of hepatic impairment on the PK of PF-06882961 over the range of clinical doses planned for future studies.

#### **4.4. End of Study Definition**

A participant is considered to have completed the study if he/she has completed all phases of the study including the follow-up visit via telephone contact shown in the schedule of activities during the period of Day 28 to Day 32 (Day 30  $\pm$ 2).

The end of the study is defined as the date of the follow-up visit via telephone contact, shown in the schedule of activities, for the last participant in the trial globally.

### **5. STUDY POPULATION**

This study can fulfill its objectives only if appropriate participants are enrolled. The following eligibility criteria are designed to select participants for whom participation in the study is considered appropriate. All relevant medical and nonmedical conditions should be taken into consideration when deciding whether a particular participant is suitable for this protocol.

Prospective approval of protocol deviations to recruitment and enrollment criteria, also known as protocol waivers or exemptions, is not permitted.

## 5.1. Inclusion Criteria

Participants are eligible to be included in the study only if all of the following criteria apply:

### 5.1.1. Participants in All Cohorts

#### Age and Sex:

1. Male and female participants between the ages of 18 (or the minimum country-specific age of consent if >18) and 70 years, inclusive, at the screening visit:
  - Refer to [Appendix 4](#) for reproductive criteria for male ([Section 10.4.1](#)) and female ([Section 10.4.2](#)) participants.

#### Type of Participant and Disease Characteristics:

2. Participants who are willing and able to comply with all scheduled visits, treatment plan, laboratory tests, lifestyle considerations, and other study procedures.

#### Weight:

3. Body mass index (BMI) of 17.5 to 38.0 kg/m^2, inclusive; and a total body weight >50 kg (110 lb), at the screening visit; with a single repeat assessment of total body weight (and hence BMI), *on a separate day* permitted to assess eligibility, if needed.

#### Informed Consent:

4. Capable of giving signed informed consent as described in [Appendix 1](#), which includes compliance with the requirements and restrictions listed in the informed consent document (ICD) and in this protocol.

### 5.1.2. Additional Inclusion Criteria for Participants without Hepatic Impairment (Cohort 1 Only)

1. At screening, no clinically relevant abnormalities identified by a detailed medical history, complete physical examination, including blood pressure (BP) and pulse rate measurement, 12-lead ECG and clinical laboratory tests, as assessed by the sponsor-identified central laboratory;
2. At screening, participants must meet the demographic-matching criteria, including:
  - A body weight that is  $\pm 10$  kg of the average of the pooled hepatic impairment cohorts (Cohorts 2, 3, and 4), as provided by the sponsor;
  - An age that is  $\pm 5$  years of the average of the pooled hepatic impairment cohorts (Cohorts 2, 3, and 4), as provided by the sponsor;

- **Attempts will be made** to ensure that the male-to-female distribution in Cohort 1, is comparable, to that in the pooled hepatic impairment cohorts (Cohorts 2, 3, and 4);
- 3. No known or suspected hepatic impairment; including at screening, meet **all** the following criteria, as assessed by the sponsor-identified central laboratory, with a single repeat permitted to assess eligibility, if needed:
  - Alanine aminotransferase (ALT)  $\leq$  upper limit of normal (ULN);
  - Aspartate aminotransferase (AST)  $\leq$  ULN;
  - Total bilirubin  $\leq$  ULN;

**NOTE:** Participants with a history of Gilbert syndrome (and hence elevated total bilirubin) are eligible provided direct bilirubin level is  $\leq$  ULN **plus** ALT and AST are  $\leq$  ULN **plus** alkaline phosphatase, hemoglobin, and reticulocyte count are all  $\leq$  ULN;

- Albumin  $\leq$  ULN;
- Prothrombin time  $\leq$  ULN.

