### **5.2.1. Participants in All Cohorts**

#### **Medical Conditions:**

1. Any condition possibly affecting drug absorption (eg, prior bariatric surgery, gastrectomy, ileal resection);

**NOTE:** Participants who have undergone cholecystectomy and/or appendectomy are eligible for this study as long as the surgery occurred more than 6 months prior to Screening;

2. At screening, participants with a positive result for human immunodeficiency virus (HIV) antibodies, as assessed by sponsor-identified central laboratory, with a single repeat permitted to assess eligibility, if needed;
3. A diagnosis of type 2 diabetes mellitus (T2DM) that is documented by medical history;
4. Personal or family history of medullary thyroid carcinoma (MTC) or multiple endocrine neoplasia syndrome type 2 (MEN2), or participants with suspected MTC per the investigator's judgement;
5. Other medical or psychiatric condition including recent (within the past year) or active suicidal ideation/behavior or laboratory abnormality that may increase the risk of study participation or, in the investigator's judgment, make the participant inappropriate for the study;

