### **5.2.2. Additional Exclusion Criteria for Participants without Hepatic Impairment (Cohort 1 Only)**

Participants presenting with any of the following will not be included in the study:

1. Evidence of chronic liver disease including history of hepatitis, hepatitis B, or hepatitis C or evidence of any of the following, as assessed by sponsor-identified central laboratory, with a single repeat, permitted to assess eligibility, if needed:
  - Hepatitis B virus, defined by presence of hepatitis B surface antigen (HBsAg);  
*NOTE:* while *not* part of the tests assessed in this study, participants with a previously positive hepatitis B surface antibody result due to vaccination are deemed eligible;
  - Hepatitis C infection, defined by presence of hepatitis C antibody (HCVAb) **and** HCV ribonucleic acid (RNA);
2. History of alcohol abuse or binge drinking and/or any other illicit drug use or dependence within 6 months of Screening. Binge drinking is defined as a pattern of 5 (male) and 4 (female) or more alcoholic drinks in about 2 hours. As a general rule, alcohol intake should not exceed 14 units per week (1 unit = 8 ounces (240 mL) beer, 1 ounce (30 mL) of 40% spirit or 3 ounces (90 mL) of wine).
3. Screening ***supine*** 12-lead ECG demonstrating QTcF interval >450 msec or a QRS interval >120 msec. If QTcF exceeds 450 msec, or QRS exceeds 120 msec, the ECG should be repeated 2 more times and the average of the 3 QTcF or QRS values should be used to determine the participant's eligibility;
4. Screening ***seated*** systolic blood pressure (SBP)  $\geq$ 140 mm Hg or diastolic blood pressure (DBP)  $\geq$ 90 mm Hg, following  $\geq$ 5 minutes of seated rest. If SBP is  $\geq$ 140 mm Hg or DBP  $\geq$ 90 mm Hg, the BP assessment should be repeated 2 more times and the average of the 3 BP values should be used to determine eligibility;
5. Use of ***chronic*** prescription medications within 7 days or 5 half-lives (whichever is longer) prior to Day 1;

***NOTE:*** Use of selected, limited prescription and non-prescription medications is permitted (refer to [Section 6.5](#) for details);

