## 10.8. Appendix 8: Child-Pugh Classification (CPC) of Liver Dysfunction

**Table 5. Scoring for Child Pugh Classification**

Cohort	CPC	Level of dysfunction	Total Score (tally based on assessment of parameters in Table 6)
1	Not Applicable	Without hepatic impairment	Not Applicable
2	A	Mild	5-6
3	B	Moderate	7-9
4	C	Severe	≥10

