**Table 6. Derivation of Child Pugh Classification Score**

Assessment Parameters	Assigned score for observed findings		
	1 point	2 points	3 points
Encephalopathy grade a (refer to Table 7 below)	0	1 or 2	3 or 4 a
Ascites	Absent	Asymptomatic	Requiring intervention
Serum total bilirubin, mg/dL	<2	2 to 3	>3
Serum albumin, g/dL	≥3.5	2.8 to 3.5	<2.8
Prothrombin time, sec prolonged	<4	4 to 6	>6

a. Participants with a prior history of Grade 3 or 4 encephalopathy who are currently receiving an intervention [*for example*: lactulose or lactitol, alone or in combination with rifaximin, and/or neomycin] to manage encephalopathy-related signs and symptoms should be scored for encephalopathy grading *based on their presentation while on intervention at the screening visit* and can be included in Study C3421014 so long as they do **not** have clinically active Grade 3 or 4 encephalopathy.

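### Cohort 1's only numeric albumin limit is an upper one, so a low albumin in a control is excluded only by judgement

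*Protocol*

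**What the plan says.** Protocol Section 5.1.2 item 3 sets out how a Cohort 1 candidate shows normal liver function. It starts "No known or suspected hepatic impairment; including at screening" and then requires all of five central-laboratory results, with one repeat allowed: ALT, AST, total bilirubin, albumin and prothrombin time, each at or below ULN. Bilirubin has an exception for Gilbert syndrome; albumin has none.

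Appendix 8 (Section 10.8), Table 6, contains the row "Serum albumin, g/dL". It gives 1 point at 3.5 or above, 2 points from 2.8 to 3.5, and 3 points below 2.8. Table 5 lists Cohort 1 as "Without hepatic impairment" and marks the score as not applicable to it.

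Three further criteria could exclude a low-albumin control, all by judgement:
- Section 5.1.2 item 1: "At screening, no clinically relevant abnormalities identified by a detailed medical history", which also covers the laboratory tests.
- Section 5.2.1 item 5: "laboratory abnormality that may increase the risk of study participation", or one that the investigator considers makes the person unsuitable.
- Section 5.2.2 item 1: "Evidence of chronic liver disease including history of hepatitis".

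**The concern.** Four of the five limits in item 3 point the right way, because ALT, AST, bilirubin and prothrombin time rise as the liver fails. Albumin falls, and the protocol's own Table 6 scores it so. The albumin line therefore does the reverse of its purpose: it turns away values that Table 6 scores as normal and admits values that Table 6 scores as abnormal. Sections 5 and 8 rule out waivers, so a healthy candidate whose albumin stays just above ULN has to be rejected.

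Cohort 1 is the single Reference for all three contrasts (Protocol Section 9.4.1.2; SAP Section 6.1.1.1), with 6 participants and at most 8 (Table 1). fu is a primary endpoint, and serum albumin is one of the hepatic-function measures against which fu and the exposure parameters are to be regressed (SAP Sections 5.2.4 and 6.1.1.2). A low-albumin control could therefore bias all three fu ratios at once, towards no effect if impairment raises fu. No size or direction is claimed for Cmax, AUCinf or AUClast.

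**Working it through.** **1. Is there a lower albumin limit elsewhere?** The places that could hold one for Cohort 1 are:

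| Place | Numeric lower albumin limit? |
|---|---|
| Protocol 5.1.2 item 3 | No, upper limit only |
| Protocol 5.2.1 item 9 (laboratory exclusions) | No; HbA1c, FPG and eGFR only |
| Protocol 5.2.2 (Cohort 1 exclusions) | No; albumin not mentioned |
| Protocol 5.2.4 (Day 1 dosing criteria) | No |
| Appendix 8, Table 5 | Child-Pugh not applied to Cohort 1 |

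**2. What the line passes.** Hold the other four Child-Pugh items at 1 point each (4 points) and add the Table 6 albumin score. The documents give no ULN for albumin; the result is the same for any ULN above 3.5 g/dL. The Table 6 bands overlap at exactly 3.5 g/dL, which is scored here as 1 point.

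| Albumin, g/dL | Meets the item 3 line? | Albumin points | Total |
|---|---|---|---|
| 4.2 or 3.5 | Yes | 1 | 4 + 1 = 5 |
| 3.4, 3.0 or 2.8 | Yes | 2 | 4 + 2 = 6 |
| 2.7 or 2.0 | Yes | 3 | 4 + 3 = 7 |

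A total of 7 lies in the Class B range (7 to 9) that defines Cohort 3. All of these candidates meet every numeric line of item 3 if the other four results are normal.

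**3. Size of the effect on fu.** The plan gives no figure to reproduce. Two assumptions are needed, neither from the documents: fu is proportional to 1/albumin, and a typical control has albumin of 4.0 g/dL. One control with albumin *a* then has fu raised by the factor 4.0/*a*. With *n* controls:

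- Reference geometric mean fu is multiplied by (4.0/*a*)^(1/*n*).
- Each Test/Reference ratio falls by 1 − 1/(4.0/*a*)^(1/*n*).

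| *a*, g/dL | 4.0/*a* | Reference, *n* = 6 | Ratio falls, *n* = 6 | Reference, *n* = 8 | Ratio falls, *n* = 8 |
|---|---|---|---|---|---|
| 3.4 | 1.176 | 1.0275 | 2.67% | 1.0205 | 2.01% |
| 3.0 | 1.333 | 1.0491 | 4.68% | 1.0366 | 3.53% |
| 2.8 | 1.429 | 1.0612 | 5.77% | 1.0456 | 4.36% |
| 2.7 | 1.481 | 1.0677 | 6.34% | 1.0504 | 4.79% |

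**4. Sensitivity to the assumed typical value (*n* = 6).** The smallest rise in the Reference mean over 2.8 to 3.4 g/dL comes from a typical value of 3.8 with a control at 3.4: (3.8/3.4)^(1/6) = 1.0187, or 1.9%. The largest comes from a typical value of 4.5 with a control at 2.8: (4.5/2.8)^(1/6) = 1.0823, or 8.2%.

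**The case against.** The strongest reply is that judgement already covers the gap. Section 5.1.2 item 1 is mandatory and covers central-laboratory tests, and Appendix 2 (Table 4) includes albumin among them. The opening of item 3 stands on its own, so the numeric list adds to it and does not replace it. To enrol a control at 2.7 g/dL, an investigator would have to consider the value neither clinically relevant nor suspicious for liver disease, with the other liver tests normal. This stands, and it makes such an enrolment unlikely. It does not justify the line: item 3 exists because the sponsor wanted objective limits as well as judgement, and sites in a multicenter study can differ on what is clinically relevant.

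The Child-Pugh tally should not be pressed. The scale grades people with liver disease, and a person with every item normal already scores 5, so a total of 6 separates nothing. The tally shows the direction of the scale; it does not diagnose a control.

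The fu figures rest on outside assumptions. The visible text does not say which plasma protein binds the drug, and it gives no between-participant SD for fu, so the shift cannot be set against the precision of the fu ratios. For scale only, Table 2 of the protocol gives a probable 90% CI of 58% to 172% for an AUCinf ratio of 100%. A low-albumin control would also show in the planned plots of fu against albumin, though that would not prevent enrolment.

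**Conclusion.** The concern holds. The albumin line in Section 5.1.2 item 3 runs opposite to Table 6 of the same protocol, and no other numeric criterion for Cohort 1 supplies a lower limit. That conclusion comes from the text alone and needs no assumption.

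The likely consequence is small. It needs at least one low-albumin control to pass several judgement criteria, and even then, under the stated assumptions, the fu ratios move by single-digit percentages. The case for correction is that an operative eligibility rule for the only Reference cohort is reversed and easy to put right, not that the study is likely to be misled.

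**What to change.** Reconcile the albumin line of Section 5.1.2 item 3 with Table 6 by making it a lower-limit condition, for example albumin at or above the central laboratory's lower limit of normal. The documents do not give that limit, and it may differ from the 3.5 g/dL at which Table 6 starts its 1-point band; the sponsor should state which is meant. Either would make a candidate at 3.0 g/dL fail on an objective criterion, provided the laboratory's limit is above that value. Keeping the ceiling beside the new floor would also close the gap, but would still reject candidates above ULN, whom Table 6 scores as normal. The other lines of item 3 can stay as they are.

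The cost is one line of protocol wording and possibly a few more control screen failures. Albumin is already in the screening panel, so no test is added, and the analyses in the SAP do not change.
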